The proposed project seeks to address knowledge gaps, represents a shift from traditional methods used to evaluate CG interventions, and has the potential to directly inform current clinical practice. Traditional treatment strategies that rely on face-to-face contact do not address practice and patient level logistical issues that are particularly relevant in dementia care. Frequent contact for monitoring and therapeutic intervention are key components in successful treatment of these patients and their informal CGs but may be taxing to the patient and family and difficult for the system to sustain.²⁵ To overcome logistical challenges we have chosen to adopt a strategy of offering brief, dementia care management, psychoeducation, and support by way of telephone assessment and intervention. Accordingly, the intervention is innovative in a number of ways. Providing CGs with the option of participating in the program over the telephone allows access to education and support without having to manage the difficulties of getting the Veteran out of the house or finding supervision for him/her in order to attend face-to-face sessions and minimizes the strain placed on the Veteran and family to find transportation to the VAMC for care. Telephone-based delivery also will enable us to serve CBOCs and rural areas using a regional, "hub and spoke" model. Both the BHL and TEP programs, which are primarily delivered via telephone, manualized (which enables CGs to work on program material at their leisure) and intended to be brief (i.e., 3 months) in duration, have been quite successful in overcoming logistical issues that might serve as barriers to engagement in interventions for Veterans in smaller clinics or rural settings.⁴⁶ These program features have the potential to result in higher CG participation and satisfaction, service utilization, improved health, and, accordingly, sustained CR independent functioning.

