Second, our stratified sampling of spousal, adult child CGs, and other family (e.g. siblings, nieces/nephews, grandchildren) will lead to more generalizable findings and help us identify subgroups of CGs for whom different intervention modalities might be most effective. Existing work on CG interventions tends to either include one type of CG (e.g., spouse, adult child) or statistically adjust for relationship type in post-hoc analyses, with few studies specifically sampling based on relationship type. While the use of homogenous CG samples in research reduces variance and potential confounding and helps generate "clean" findings that are more easily interpreted, this is done at the expense of generalizability of the findings. Moreover, the finding that spousal, adult child, and other family CGs represent distinct groups with different caregiving experiences and patterns of enrollment, attrition, and outcomes, highlights the value of examining how different family CGs respond to individual vs. group intervention. Modeling the moderating role of relationship type in the association between different intervention modalities and outcomes can help inform future studies and shed light on ways to tailor CG interventions to ensure participant retention and maximum impact.

H. Purpose of the Project: (Clearly provide the purpose of this research project.) **The purpose of the project is to: a) test the comparative effectiveness of 2 delivery models (individual TEP + individual care management vs. group TEP + individual care management) of a telephone-based, collaborative dementia care intervention for caregivers (CGs), and b) explore whether the individual or individual + group intervention is more effective/acceptable among spousal vs. adult children/other family member CGs.**

I. Describe the Research Questions or Hypotheses (that is, what questions are you trying to address by conducting the research.)

Aim 1: What is the relative impact of usual care (UC) vs. collaborative care and support delivered in either a group or individual format on CG and CR outcomes?

-We hypothesize that both the group and individually delivered interventions will be superior to UC, with the group delivered intervention (which will include both TEP group sessions and individual care management calls with CGs) resulting in the greatest changes in outcomes over time: group > UC (Hyp1A); individual > UC (Hyp1B); group > individual (Hyp1C).

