4.1. Include statistical power calculations and the assumptions made in making these calculations. **Power calculations were computed for Aims 1 and 2. We assumed the availability of 405 participants that are eligible and agree to participate in the study. For the purposes of the power analysis, we considered 3 outcome measures (CG distress in response to dementia symptoms (RMBPC), CG burden (ZBI), and overall CG mental wellbeing (MCS subscale of VR16)). The power analysis, conducted using PASS v12, was based on the linear mixed effects model that considers the correlation among 4 repeated measures per CG and interactions between intervention group, time and CG type. The power analysis also took into consideration the following additional factors: 1) 10% drop-out; 2) adjusted 2-sided significance level of 0.017 due to multiple outcome measures which is a conservative approach; and 3) 80% power. In Aim 1, the primary interest is the interaction effects between time and intervention group. Assuming a 0.2 standardized decline in outcome within individuals over time, a correlation of 0.75 between repeated measures within an individual, and a total sample size of 360 after 10% drop-out, the study has 80% power to detect a 0.4 effect size {or larger} between the largest and smallest effects associated with intervention groups. In Aim 2, the primary interest is to examine the impact of the CG and CR relationship on outcomes which will be modeled as a three-way interaction between time, intervention group and CG/CR relationship. The power for Aim 2 is estimated using the same assumptions as in Aim 1, but with a sample size of 180. The study has 80% power to detect an effect of 0.66 between intervention groups within one type of CG/CR relationship. From a clinical significance standpoint, an effect of 0.4 equates to a mean of 4.6 (VR16), 3.6 (NPI), and 5.2 (RMBPC) points using data (i.e., SDs) from our pilot work. Of note, prior meta-analytic work suggests that improvements of 0.4-0.5 standard deviations on measures of CG outcomes are considered *clinically meaningful* effects and indicative of "study success", regardless of statistical significance.¹⁻³ Thus, we are confident that we will have power sufficient to detect clinically meaningful effects.**

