Outcomes: In order to analyze the degree to which randomization group is associated with changes in our three primary outcomes (i.e., CG distress in response to CR dementia-related symptoms, CG burden, and CG mental functioning) over time (Hyp 1A-1C), we will run three separate intent-to-treat, mixed effects linear regression models (using SAS PROC MIXED). Mixed models account for multiple observations and make use of all available data for each CG (regardless of drop-out or missing assessment periods), account for subject-level clustering, and accommodate modeling of contemporaneous and lagged effects and time variant and invariant variables. Specifications for the mixed models will include random effect estimates for intercept and slope (i.e., time) to account for within-individual variability. We will specifically test for group by time interactions. All models will control for baseline scores for the respective outcome and covariates identified during the preliminary analysis phase. It is important note that while these three variables are our primary outcomes, we also will run post-hoc mixed models (including mixed effects logistic models for binary outcomes; SAS PROC NLMIXED) to examine the relative impact of the intervention on other outcomes including CR frequency of NPI and RMBPC symptoms, CR IADL/ADLs, CG engagement in VA and non-VA services, and inpatient/outpatient costs (cost data will be analyzed using a Gamma distribution). Corrections will be made for multiple comparison effects.

Specific Aim 2-Evaluating the Moderating Role of CG-CR Relationship Type: In order to examine the moderating role of CG-CR relationship type on study/intervention engagement (Hyp 2A) and our 3 primary outcomes (Hyp 2B), we will again run the linear and logistic mixed effects models outlined above, and include estimation of random effects for both intercepts and slopes, as well as all main effects, relationship type*time interactions, and relationship type*randomization group*time interactions (i.e., all 2- and 3-way interactions). We also will run logistic regression models examining whether consent and engagement in each of the study arms for eligible CGs varies as a function of relationship type.

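### Aim 1 names only a group-by-time test and leaves open the response rows, the coding of time and the arm contrast that decides each of Hyp 1A to 1C

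*Combined protocol and SAP*

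**What the plan says.** - **Hypotheses (section I, Aim 1).** Three pairwise claims, with the group-delivered arm expected to do best: "resulting in the greatest changes in outcomes over time: group > UC (Hyp1A); individual > UC (Hyp1B); group > individual (Hyp1C".
- **Power (section V.4.1).** The model "considers the correlation among 4 repeated measures per CG", and for Aim 1 "the primary interest is the interaction effects between time and intervention group". The 0.4 effect is the gap "between the largest and smallest effects associated with intervention groups". Assessments are at baseline and at 3, 6 and 12 months (section N.1.1 A), so four measures per caregiver must include baseline.
- **Analysis (section V.4.2, Aim 1).** "We will specifically test for group by time interactions. All models will control for baseline scores for the respective outcome". The models carry "random effect estimates for intercept and slope (i.e., time". The section cites Hyp 1A to 1C and promises corrections for multiple comparisons. It gives no response rows, no coding of the fixed time effect, and no arm contrast or visit for any hypothesis.
- **Aim 2B (section V.4.2, Aim 2).** Moderation is tested through "relationship type*randomization group*time interactions (i.e., all 2- and 3-way interactions".
- **Program length.** The rationale describes the parent programs as "intended to be brief (i.e., 3 months) in duration". Section L.3.2 gives up to 3 months of care management, and follow-up is timed from baseline (section N.1.2).

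**The concern.** Several models fit the text, and they ask different questions. If baseline is one of four responses, group by time includes the change from baseline to month 3, when the program is delivered. If baseline is only a covariate and the responses are months 3, 6 and 12, group by time compares trends after month 3. A benefit reached by month 3 and held then sits in the arm main effect, which the plan does not name as an Aim 1 test. Time coded as linear or as categorical changes the answer again.

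Nor does a three-arm interaction test by itself decide three pairwise, directional hypotheses.

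At stake is whether the same data count as a positive Aim 1 result. The timeline in section N.2.2 foresees periodic merging of the randomization assignments and interim as well as final analyses, so the choice could be made after outcome data are seen. Aim 2B inherits the gap because its test is also an interaction with time.

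**Working it through.** **Inputs from section V.4.1.** 360 caregivers after dropout, so n = 120 per arm (405 × 0.9 = 364.5, close to 360); correlation 0.75; two-sided alpha 0.017, critical z = 2.387; unit SD. Visits are at 0, 3, 6 and 12 months.

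**Assumptions.** The documents give no expected arm trajectory. Pair differences at months 3/6/12 are assumed to be: held 0.4/0.4/0.4; half fade 0.4/0.4/0.2 or 0.4/0.3/0.2; linear growth 0.1/0.2/0.4; and a smaller held 0.2/0.2/0.2. Random-slope variance is zero unless stated. The within-person residual variance is 1 − 0.75 = 0.25.

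**The plan's own figure.** The stated 80% for a 0.4 range cannot be uniquely reproduced, because the shape of the effect over visits is not given. The four-row group-by-time variants tried gave 83% to 99.7%. I do not call the 80% wrong.

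**1. Four-row linear slope, one arm pair.** Mean time is 5.25 and Σ(t − 5.25)² = 78.75. SE = √(2 × 0.25 / (120 × 78.75)) = 0.00727.
- Held 0.4: slope difference 0.4 × 5.25 / 78.75 = 0.02667, z = 3.67, power 90%.
- Half fade: 0.75 / 78.75 = 0.00952, z = 1.31, 14%; or 0.675 / 78.75 = 0.00857, z = 1.18, 11%.
- Growth: 0.4 / 12 = 0.03333, z = 4.58, 99%.
- Held 0.2: z = 1.83, 29%.

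The three-arm, 2-df version with arms at 0/0.2/0.4 has noncentrality 3.67² ≈ 13.4 and 83% power for the held pattern.

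**2. Four-row categorical group by time, one pair, 3 df.** Noncentrality = (120/2) × Σ(d − mean d)² / 0.25, over the four visits with d = 0 at baseline.
- Held 0.4: 60 × 0.12 / 0.25 = 28.8, 99%.
- Half fade: 60 × 0.11 / 0.25 = 26.4, 99%; or 60 × 0.0875 / 0.25 = 21.0, 95%.
- Growth: 21.0, 95%.
- Held 0.2: 7.2, 44%.

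**3. Linear group by time on follow-up rows, baseline as covariate.** Mean time is 7 and Σ(t − 7)² = 42. SE = √(2 × 0.25 / (120 × 42)) = 0.00996. With equal correlations the baseline covariate does not alter the slope.
- Any held benefit: slope difference 0, so the rejection rate is alpha, 1.7%.
- Growth: 0.03333 / 0.00996 = 3.35, 83%.
- Half fade 0.4/0.3/0.2: (−4 × 0.4 − 1 × 0.3 + 5 × 0.2) / 42 = −0.0214, z = −2.15, 41%. This rejection signals loss of benefit.

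**4. Baseline-adjusted mean of months 3, 6 and 12, one pair.** Variance = (1 + 2 × 0.75)/3 − 0.75² = 0.2708. SE = √(2 × 0.2708 / 120) = 0.0672.
- Held 0.4: z = 5.95, over 99%.
- Half fade: 0.333 / 0.0672 = 4.96, 99.5%; or 0.300 / 0.0672 = 4.47, 98%.
- Growth: 0.233 / 0.0672 = 3.47, 86%.
- Held 0.2: z = 2.98, 72%.

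| Assumed pattern (one pair) | Four-row slope | Four-row categorical | Follow-up-only slope | Adjusted mean |
|---|---|---|---|---|
| Held 0.4 | 90% | 99% | 1.7% | over 99% |
| Half fade | 11–14% | 95–99% | tests loss | 98–99.5% |
| Growth to 0.4 | 99% | 95% | 83% | 86% |
| Held 0.2 | 29% | 44% | 1.7% | 72% |

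**Sensitivity.** With random-slope SD s per month, the four-row slope SE is √((2/120)(0.25/78.75 + s²)). For s = 0.02, 0.03 and 0.04, held-0.4 power falls to 86%, 80% and 73%; the adjusted mean stays above 99%. At correlation 0.5 (assumed) and no random slope, held 0.4 gives 58% for the four-row slope and 99% for the adjusted mean.

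**The case against.** The strongest reply is that the plan points to keeping all four rows. Section V.4.1 makes the interaction the Aim 1 interest in a four-measure model, and section V.4.2 speaks of change over time using all available data. Adding baseline as a covariate as well is awkward but fits both sections. In 3,000 to 6,000 simulated trials that hybrid with linear time had 88–89% power for a held 0.4 SD with a random intercept only, and about 82% to 65% when a random slope was fitted (true slope SD 0 to 0.04). This stands. A reader might infer that the planned test has only alpha-level power for a held benefit, or that the two sections contradict each other. The documents support neither: 1.7% belongs to the reading that section V.4.1 supports least, and section V.4.2 never says baseline is a covariate only.

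A reader might also infer that keeping baseline as a response misses a fading benefit. That follows from linear time, not from the baseline row: categorical time gives 95–99%. The random slope suggests linear time but does not settle the fixed effect.

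Growth after month 3 is possible too. Groups of 5 to 8 might run past the month 3 visit, and members may share contact details. Under growth the slope beats the adjusted mean, so choosing that mean is partly a preference.

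The reply does not close the gap. Follow-up rows with baseline as covariate is an ordinary reading of controlling for baseline, and even with four rows no contrast decides Hyp 1A, 1B or 1C. Citing the hypotheses and promising multiplicity corrections does not supply one.

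**Conclusion.** The concern holds as an unresolved specification that should be fixed. For the same assumed held benefit of 0.4 SD, readings the text permits range from 1.7% to 99% power. For a half-faded benefit, four-row readings range from 11–14% (linear) to 95–99% (categorical). The 0.4 SD is the section V.4.1 gap between the extreme arms, so at least one other pair will usually be closer. At a held 0.2 SD the four-row tests have 29% and 44%, against 72% for the adjusted mean.

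The sizes rest on the section V.4.1 inputs, zero random-slope variance except where stated, and trajectories that are assumptions. The missing rows, coding and contrasts do not depend on those assumptions.

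**What to change.** In section V.4.2:
- State that the responses are the 3, 6 and 12 month scores, that visit is categorical, and that baseline score is a covariate only.
- Decide each of Hyp 1A, 1B and 1C by one named baseline-adjusted arm contrast, fixed before data are seen. The mean of months 3, 6 and 12 is one choice; another named contrast would also close the gap.
- Report the contrast at each visit and keep the linear slope as supportive.
- Say which alpha applies to each contrast. The 0.017 covers three outcomes only (0.05/3). If it were also split over three pairs (0.05/9 = 0.0056), power of the adjusted mean for a held 0.2 SD falls from 72% to 58%.
- Test Aim 2B as relationship type by arm on the same contrast.

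In section V.4.1, restate power for that contrast and for each arm pair.

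The cost is wording and PROC MIXED code. The downside is slow growth: 86% for the mean contrast against 99% for the four-row slope, or 83–75% against 97–91% with random-slope SD 0.02–0.04.

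Separately, and independent of the interaction question, the preliminary-analysis rule in section V.4.2 picks covariates by imbalance tests. Replace it with pre-specified covariates that always include relationship type, the randomization stratum, in the Aim 1 models. Stratification aims to balance that factor, so an imbalance rule is unlikely to select it.

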Aim 2: Does the relationship between the CG and CR differentially impact the relative acceptability (Aim 2A) and efficacy (Aim 2B) of the group vs. individually delivered intervention (i.e., moderation model)?

-We anticipate that the group intervention will be associated with higher intervention engagement rates (Hyp2A) and be more effective (Hyp2B) among spousal, relative to adult child/other family, CGs.

J. Primary Outcome Variable(s): (Define the primary outcome variable(s) used to support the study objectives (e.g. if the objective is to show that treatment A is superior to treatment B in the treatment of subjects with essential hypertension, the primary outcome variable is blood pressure measurement.) **CG burden and CG distress in response to CR dementia-related symptoms**

K. Secondary Outcome Variable(s): (Define the secondary outcome variables. Such measured variables should also include the timing of measurement.) **Overall CG mental health (VR 16)**

L. Study Design and Methods:

1. Is this a clinical trial? YES NO

1.1. If yes, what type? Check all that apply.

Phase I Phase II Phase III Phase IV

1.2. If yes, this study must be registered on Clinicaltrials.gov.

2. Design

2.1. What research methods will be used in the project? Check all that apply.

 Surveys/Questionnaires	 Interviews	 Audio Taping
 Behavioral Observations	 Chart Reviews	 Video Taping
 Focus Groups	 Randomization	 Double-Blind
 Control Group	 Placebo	 Withhold/Delay Treatment
 Specimen Collection	 Deception	 Telephone Survey
 Other (Describe)		

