2.2. Describe how randomization or other treatment assignment will be made. **Once inclusion/exclusion criteria are met, we will use a random number table that will be generated using the PROC PLAN macro in SAS v9.3 to randomly assign equal numbers of CGs to the individual TEP + individual care management, group TEP + individual care management, or UC arms. The randomization program will take into account stratification by relationship type (spouse/partner, adult child/other family). This will yield 135 CGs per arm (90 spouses/partners, 45 adult children/other family). We will enroll more spousal CGs than adult children/other family CGs because this distribution more closely reflects the demographic composition of CGs providing care for Veterans with dementia found in our preliminary work.**

2.3. For retrospective research studies, provide the "look-back" period. (e.g., December 1, 1999 through December 31, 2008.) **This is primarily a prospective study. However, for the medical chart review component of the project, data from**

Veterans' medical charts will be extracted for a period of one year prior to the CGs' 3 month research assessment date.

3. Study Duration

- 3.1. Provide the estimated length of time to enroll all subjects and complete the study. **4 years**
- 3.2. Explain the expected duration of subject participation including any follow-up. **Research assessments will be conducted at baseline and 3, 6, and 12 month followup. If randomized to a treatment arm, CGs will receive up to 3 months of care management services.**
- 3.3. Specify the projected date of completion of the proposed study. **February 2019**

4. Drug Information (If not applicable state, "Not Applicable.") Not Applicable

- 4.1. Specify if the drug or biological agent is:
 - 4.1.1. FDA approved **N/A**
 - 4.1.2. Used for off-label purposes **N/A**
 - 4.1.3. Not yet FDA approved. **N/A**
- 4.2. Include the FDA Investigational New Drug (IND) number for all non-FDA approved and off-label drugs, biological agents or nutritional supplements. If not applicable state, "Not Applicable." **N/A**
- 4.3. Provide all relevant information about the drug **N/A**
- 4.4. Explain any wash-out periods, rescue medications permitted and any type of medications not permitted while enrolled in the study. **N/A**
- 4.5. Describe blinding and un-blinding procedures. **N/A**

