- a) Individual Delivered TEP Arm:** Based on evaluation of the baseline interview, the CG and care manager will work together to determine which of the modules are most appropriate for the CG. In addition to two mandatory modules that cover the stages of dementia and provide a brief introduction to problem solving techniques, action plan development, and coping skills, CGs can select from a menu of additional modules covering various content areas evaluated during the course of the monthly assessments (e.g., communication skills, behavioral management techniques, stress management and coping skills, long-term planning, etc.). Each individual TEP session will begin with reviewing education related to the selected module. The remainder of each session will involve coaching the CG on emotion-focused and problem-focused coping strategies. The care manager will also discuss problem solving with the CG to reinforce the action plan and the educational component of the intervention. Each session will be delivered over the telephone and will last 40 minutes-1 hour. Sessions will occur approximately every other week, depending upon the availability and preference of the CG. The number of TEP contacts will depend on the number of topics chosen and covered.
- b) Group Delivered TEP Arm:** CGs assigned to this arm will be asked to participate in all TEP modules in a group format. Each call will take up to 1.5 hours. Each group will be comprised of 5-8 CGs who will call into a VANTS teleconference line at a pre-specified time. The content of the calls will mirror those in the individual TEP delivered program. As with the individual

TEP delivered program, each session will begin with reviewing a different education topic and the remainder of the call will involve reviewing weekly action plans, discussion of emotion and problem focused coping strategies, and skills training. This arm, however, will include the added component of peer group support. CGs will be given the option of sharing their contact information with one another. CGs will be asked to complete their workbooks prior to the next session.

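### Hyp 2A models engagement with a 3-month intervention on a 0 to 12 month time axis, and no stated analysis validly tests whether relationship type moderates group versus individual engagement

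*Combined protocol and SAP*

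**What the plan says.** Section I (Aim 2) asks whether relationship type affects the relative acceptability of the group and individual formats. Its hypothesis begins "We anticipate that the group intervention will be associated with higher intervention engagement rates (Hyp2A") and goes on to name spouses relative to adult child and other family caregivers. Section V.4.2 renames the endpoint, referring to the "moderating role of CG-CR relationship type on study/intervention engagement (Hyp 2A"). No section gives engagement a unit, denominator, threshold or time window.

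For the analysis, V.4.2 states "we will again run the linear and logistic mixed effects models outlined above, and include estimation of random effects for both intercepts and slopes", together with relationship-by-time and relationship-by-arm-by-time terms. The Aim 1 models it refers back to define the slope as time and control for the baseline score of the outcome. A further sentence adds logistic regressions of consent and engagement in each study arm by relationship type, with no time term stated.

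On duration, L.3.2 says "If randomized to a treatment arm, CGs will receive up to 3 months of care management services", with assessments at baseline, 3, 6 and 12 months. The timeline in N.2.2 gives care management and TEP together a 3-month duration.

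On the load offered, N.1.1.C.ii differs by arm. Group arm: "CGs assigned to this arm will be asked to participate in all TEP modules in a group format". Individual arm: "In addition to two mandatory modules that cover the stages of dementia" and introduce problem solving, further modules come from a menu; "the CG and care manager will work together to determine which of the modules are most appropriate for the CG", and "The number of TEP contacts will depend on the number of topics chosen and covered".

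**The concern.** Hyp 2A is one of the two named hypotheses of Aim 2. Attendance at a short programme is essentially one quantity per caregiver, observed once the programme has ended. A model built on change across four visits has no use for it: there is no baseline score to control for, no trajectory after month 3, and no sessions in the usual care arm.

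If the interaction with time is taken as the test, its sign and size depend on how the analyst fills the visits where engagement cannot occur. If the analyst turns to the extra logistic regressions, they describe spouses against others inside one arm at a time, and say nothing formal about whether that gap differs between formats. Aim 2A would then rest on choices made after the data are in. One natural choice, sessions attended over sessions chosen, is not comparable between the arms.

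**Working it through.** The documents give no rate, effect size or power for engagement, so there is no figure of their own to reproduce.

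**1. Where intervention engagement can exist.** Three arms by four visits gives 12 cells. The value is absent at baseline (3 cells), at 6 and 12 months (6 cells) and in usual care at 3 months (1 cell). That leaves 12 − 10 = 2 cells: the two active arms at month 3. One informative value per caregiver cannot support both a random intercept and a random slope.

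**2. What the relationship-by-arm-by-time coefficient would measure.** Suppose the true moderation is 0.20 (20 points, illustrative), time is linear in months and data are complete. The fixed-effect slope of each cell is then the least-squares slope, Σ(t − t̄)y / Σ(t − t̄)².

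- Visits 0, 3, 6, 12: t̄ = 5.25; deviations −5.25, −2.25, 0.75, 6.75; sum of squares 78.75.
  - Zeros outside month 3: −2.25/78.75 × 0.20 = −0.0057 per month.
  - Value carried forward from month 3: (−2.25 + 0.75 + 6.75)/78.75 × 0.20 = +0.0133 per month.
- Visits 3, 6, 12, with a constant zero as the baseline covariate: t̄ = 7; deviations −4, −1, 5; sum of squares 42.
  - Zeros after month 3: −4/42 × 0.20 = −0.0190 per month.
  - Value carried forward: (−4 − 1 + 5)/42 × 0.20 = 0.

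The same data give a negative, positive or null coefficient. V.4.2 also says that all two-way interactions are included, so a relationship-by-arm term is present. With time counted from baseline, however, that term is the contrast at month 0, when nothing has been delivered.

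**3. The extra logistic regressions.** As worded, they ask within each arm whether engagement varies by relationship type. No arm-by-relationship contrast is named.

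**4. Why the definition matters.** Assume 10 group sessions (range 8 to 12; the background describes the existing group TEP as a 10-week programme), with spouses attending 7 and others 5 in both formats, and individual-arm caregivers choosing what they attend. Attended over chosen gives 7/10 − 5/10 = 20 points in the group arm and 100% − 100% = 0 in the individual arm. That is a false moderation of 20 points (2/8 = 25 points with 8 sessions; 2/12 = 16.7 with 12).

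Simulated trials used 90 spouses and 45 others per active arm (L.2.2), the same attendance behaviour in both formats, 10 modules, 70% against 50% attendance and a two-sided 0.05 interaction test:

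| Engagement defined as | Trials with a false interaction |
|---|---|
| Attended/chosen, overdispersed attendance | 56 to 65% |
| Attended/chosen, binomial attendance, chosen equal to attended (minimum 2) | 100% |
| Session count, no cap in either arm | 5 to 6% |
| Session count, individual arm limited to about 6 | 30 to 31% |
| At least 2, or at least 4, sessions (overdispersed attendance) | about 5% |

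The cap of about 6 comes from sessions every other week over roughly 13 weeks (13/2 = 6.5). At 70% against 60%, attended/chosen gives 19 to 37% across 8 to 12 modules with overdispersed attendance, and 94% with binomial attendance and 10 modules. When the relationship types attend equally (6 and 6 sessions, binomial attendance), it gives 5.5%, so no artefact.

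**The case against.** The strongest reply is that V.4.2 speaks of study as well as intervention engagement, and covers Hyp 2A and Hyp 2B in one sentence. Study engagement, meaning completion of the follow-up assessments, does recur over time, and a time-based model can serve it. That stands, but Hyp 2A in section I concerns engagement with the intervention.

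A second reply is that Hyp 2A, read literally, compares spouses with others receiving the group format. The per-arm logistic regressions would answer that, under a single denominator rule. The wording allows this reading. Aim 2A, however, asks about group versus individual delivery, and section H frames the question as which format is more acceptable to which caregivers. The within-arm results do not test that.

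A reader might infer something stronger: that the plan fixes the denominator in one arm, lets the caregiver choose it in the other, and so will manufacture the hypothesised moderation. The documents do not support this. No definition of the rate is given, and the naming of logistic models may point to a yes/no endpoint. Individual-arm modules are chosen jointly with the care manager, above a floor of two. The artefact also needs relationship types to differ in attendance. The background makes that plausible (adult children are described as more likely to drop out) but does not quantify it.

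**Conclusion.** The concern holds for the model. As written, Hyp 2A is assigned time and baseline terms that have no meaning for intervention engagement, and the only other stated analysis does not make the group-versus-individual comparison in Aim 2A. This follows from the text and the visit schedule. The coefficients of −0.019 to +0.013 per month for one and the same 20-point moderation show the consequence, assuming linear time and complete data.

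The denominator problem is conditional. It arises if engagement is taken as attended over chosen, or as a raw count with fewer sessions available in one arm, and if relationship types differ in attendance. The false-positive rates rest on assumed session counts, attendance levels and spread, and are illustrative only. They are a reason to define the endpoint, not an estimate of error in this trial.

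The primary outcomes, Aim 1 and Hyp 2B are not affected. Section H presents the relationship-type question as exploratory, so this should be corrected but does not threaten the main result.

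**What to change.** In V.4.2, Specific Aim 2:

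- Keep the time-based mixed models for the primary outcomes (Hyp 2B) and, if wanted, for study retention, named as a separate endpoint.
- For intervention engagement, define one value per caregiver over the 3-month intervention period. Analyse the two active arms only, by logistic (binomial) regression on arm, relationship type and arm-by-relationship. State that the interaction is the Hyp 2A test.
- Give the value the same denominator in both arms, for example completion of the two mandatory TEP modules, or a minimum-session indicator set at a number attainable in both arms. Do not use sessions attended over sessions chosen.
- Report total TEP sessions and care-manager calls by arm descriptively.

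The cost is wording; N.1.1.C.i already has care managers log each contact with caregivers. The downside is that elective modules leave the test, and power is limited. In simulations assuming a true 20-point moderation of TEP attendance, power was about 54 to 57% with the two mandatory modules. Adding the three care-manager calls at about 2, 5 and 9 weeks lowered it to about 30 to 41% (assuming 80 to 90% completion, unrelated to format), because those calls are delivered individually in both arms. They are better reported separately.
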